2 STUDY DESCRIPTION

2.1 Study Design

This study is a Phase 1, open-label, dose escalation study to evaluate the safety, tolerability, PK, and PD and preliminary anti-tumor activity of cabiralizumab as monotherapy in subjects with advanced solid tumor. In addition, the study will evaluate the safety profile, PK, PD and preliminary anti-tumor activity of cabiralizumab in combination with nivolumab in subjects with advanced solid tumors and hematologic malignancies.

For the monotherapy cohorts of the study, cabiralizumab will be given on Day 1 of each 14-day treatment cycle until the progression of disease, discontinuation due to toxicity, withdrawal of consent or study closure. For the combination cohorts of the study, cabiralizumab and nivolumab will be given on Day 1 of each 14-day treatment cycle until the progression of disease, discontinuation due to toxicity, withdrawal of consent or study closure. Nivolumab will be administered as an IV infusion over 30 minutes, and then cabiralizumab will be administered as an IV infusion over 30 minutes.

This study consists of 2 planned cabiralizumab monotherapy cohorts (M1: 2 mg/kg and M2: 4 mg/kg) and 2 cohorts of cabiralizumab in combination with nivolumab (C1: 4 mg/kg cabiralizumab and 3 mg/kg nivolumab in subjects with solid tumors and C2: 4 mg/kg cabiralizumab and 3 mg/kg nivolumab in subjects with hematologic malignancies).

The study will consist of 3 periods: Screening, Treatment and Follow-up. The study will end after the last subject completes the last visit.

Screening begins by establishing the subject's initial eligibility and signing of the informed consent form (ICF). Subjects must have treatment assignment within 28 days after signing the informed consent.

The Treatment Phase begins when the treatment cohort is assigned to the subjects. The subject will be assigned to the open cohort (M1, M2, C1, or C2) at the timing of the treatment assignment. First dose should be started within 3 days of treatment assignment. The subjects will be required to be hospitalized for safety evaluation at least for 8 days from the first dose. The subjects can be discharged at the investigator's discretion at Day 8.

The Follow-Up Phase begins when the decision to discontinue a subject from all treatment is made. Subjects will be followed for drug-related toxicities until these toxicities resolve, return to baseline, or are deemed irreversible. All adverse events will be documented for a minimum of 100 days after the last dose of study medication. The study design schematic is presented in Figure 2.1-1 and Figure 2.1-2.

Figure 2.1-1: Dose Escalation Schematic

[figure not shown]
[figure not shown]

Figure 2.1-2: Study Design Schematic

2.2 Treatment Assignment

The selection and timing of dose for each participant is as follows:

Table 2.2-1: Selection and Timing of Dose

Cohort	Study Treatment	Unit dose strength(s)/Dosage level(s)	Dosage formulation Frequency of Administration	Route of Administration
M1*	Cabiralizumab	2 mg/kg	Every 2 weeks	Intravenous
M2	Cabiralizumab	4 mg/kg	Every 2 weeks	Intravenous

Table 2.2-1: Selection and Timing of Dose

Cohort	Study Treatment	Unit dose strength(s)/Dosage level(s)	Dosage formulation Frequency of Administration	Route of Administration
C1/C2	Cabiralizumab	4 mg/kg	Every 2 weeks	Intravenous
	Nivolumab	3 mg/kg	Every 2 weeks	Intravenous

*: A lower dose may be tested if appropriate.

Sponsor has the option to expand combination cohorts (up to 12 subjects in total per each combination cohort) at the dose previously established to be safe in order to obtain additional data or to investigate alternative dose levels to those defined in the protocol.

No within-subject dose escalations will be permitted. If a dose level is found to exceed the MTD subjects enrolled in that dose level may be treated at a lower dose following consultation and agreement between Investigators, the Sponsor and Efficacy and Safety Review Committee.

2.3 Blinding and Unblinding

Not Applicable.

2.4 Protocol Amendments

This SAP incorporates the following revised protocols.

Table 2.4-1: Revised Protocols

No	Date of Issue	Summary of Major Changes
Original	17-Jan-2017	
Revised 01	08-Mar-2017	Added clarification of DLT evaluable participants etc.
Revised 02	06-Jul-2017	Added clarification of the allowance on treatment phase procedural outline etc.
Revised 03	12-Sep-2017	DLT criteria incorporated with other ongoing studies.
Revised 04	17-Oct-2017	Removed Survival follow up after Follow up Period.
Revised 05	22-Mar-2018	Added Clarification in bone marrow sample for efficacy assessments in subjects with Multiple Myeloma

3 OBJECTIVES

3.1 Primary

- To assess the safety and tolerability of cabiralizumab as monotherapy in subjects with advanced solid tumors.

3.2 Secondary

- To assess the safety of cabiralizumab in combination with nivolumab in subjects with advanced solid tumors and hematologic malignancies.
- To characterize the PK profile of cabiralizumab administered alone and in combination with nivolumab.
- To characterize the immunogenicity of cabiralizumab and nivolumab
- To assess the preliminary anti-tumor activity of cabiralizumab administered alone and in combination with nivolumab in subjects with advanced solid tumors.
- To assess the preliminary anti-tumor activity of cabiralizumab administered in combination with nivolumab in subjects with hematologic malignancies.

4 ENDPOINTS

4.1 Primary Endpoints

The assessment of safety of cabiralizumab as monotherapy will be based on the incidence of adverse events (AEs), serious adverse events (SAEs), adverse events leading to discontinuation, adverse events leading to dose modification, other events of interest (OEOI), and deaths. In addition clinical laboratory tests, and immunogenicity (i.e. development of anti-drug antibody) will be analyzed.

4.2 Secondary Endpoints

4.2.1 Safety of Cabiralizumab in Combination with Nivolumab

Same as Section 4.1.

4.2.2 Preliminary Antitumor Activity in Subjects with Advanced Solid Tumors

The following set of study-level efficacy endpoints will be used for comprehensive assessment of antitumor activity.

4.2.2.1 Objective Response Rate

Objective Response Rate (ORR) is defined as the number of treated subjects who achieve a best response of complete response (CR) or partial response (PR) based on investigator assessments (using RECIST v1.1 criteria) divided by the number of all treated subjects. Best Overall Response (BOR) is defined as the best response, as determined by the investigator, recorded between the date of first treatment and the date of objectively documented progression per RECIST v1.1 criteria or the date of subsequent therapy, whichever occurs first. For subjects without documented

progression or subsequent therapy, all available response designations will contribute to the BOR determination. Confirmation of response is required at least 4 weeks after the initial response.

4.2.2.2 Duration of Response

Duration of Response (DOR) is defined as the time between the date of first documented response (CR or PR) to the date of the first documented tumor progression as determined by the investigator (per RECIST v1.1 criteria), or death due to any cause, whichever occurs first. Subjects who start subsequent therapy without a prior reported progression will be censored at the last evaluable tumor assessments prior to initiation of the subsequent anticancer therapy. Subjects who die without a reported prior progression will be considered to have progressed on the date of their death. Subjects who neither progress nor die, DOR will be censored on the date of their last evaluable tumor assessment. DOR will be evaluated for responders (confirmed CR or PR) only.

4.2.3 Preliminary Antitumor Activity in Subjects with Hematologic Malignancies

The following set of study-level efficacy endpoints will be used for comprehensive assessment of antitumor activity.

4.2.3.1 Objective Response Rate

Objective Response Rate (ORR) is defined as the number of treated subjects who achieve a best response of stringent complete response (sCR), complete response (CR), very good partial response (VGPR) or partial response (PR) based on investigator assessments (using IMWG Response criteria) divided by the number of all treated subjects.

4.2.3.2 Duration of Response

Duration of Response (DOR) is defined as the time between the date of first documented response (sCR, CR, VGPR or PR) to the date of the first documented tumor progression as determined by the investigator (per IMWG Response criteria), or death due to any cause, whichever occurs first. Subjects who start subsequent therapy without a prior reported progression will be censored at the last evaluable tumor assessments prior to initiation of the subsequent anticancer therapy. Subjects who die without a reported prior progression will be considered to have progressed on the date of their death. Subjects who neither progress nor die, DOR will be censored on the date of their last evaluable tumor assessment. DOR will be evaluated for responders (confirmed sCR, CR, VGPR or PR) only.

Validated ADA test methods enable characterization of samples into ADA-positive vs ADA-negative. To classify the ADA status of a participant using data from an in vitro test method, each sample from a participant is categorized based on the following definitions:

Table 4.3.3-1: Sample ADA Status

Sample ADA Status	Definition
Baseline ADA-positive sample	ADA is detected in the last sample before initiation of treatment
Baseline ADA-negative sample	ADA is not detected in the last sample before initiation of treatment
ADA-positive sample	1) an ADA detected (positive seroconversion) sample in a participant for whom ADA is not detected at baseline, or (2) an ADA detected sample with ADA titer to be at least 4-fold or greater (\geq) than baseline positive titer
ADA-negative sample	After initiation of treatment, ADA not positive sample relative to baseline

Next, using the sample ADA status, participant ADA status is defined as follows:

Table 4.3.3-2: Participant ADA Status

ADA Status	Definition
Baseline ADA-positive	A participant with baseline ADA-positive sample
ADA-positive	A participant with at least one ADA positive-sample relative to baseline at any time after initiation of treatment
• Persistent Positive (PP)	ADA-positive sample at 2 or more consecutive timepoints, where the first and last ADA-positive samples are at least 16 weeks apart
• Not PP-Last Sample Positive	Not persistent positive with ADA-positive sample at the last sampling timepoint
• Other Positive	Not persistent positive with ADA-negative sample at the last sampling timepoint
ADA-negative	A participant with no ADA-positive sample after the initiation of treatment

They are applicable for both Cabiralizumab and Nivolumab.

5 SAMPLE SIZE AND POWER

This is a Phase 1 safety study and the sample size cannot be precisely determined and depends on the observed toxicities. Between 6 and 12 participants are expected to be treated during dose escalation (Part 1), assuming 2 mg/kg and 4 mg/kg cabiralizumab monotherapy are explored. On the combination cohorts, 6 subjects each cohort are expected to be treated with 4 mg/kg cabiralizumab in combination with 3 mg/kg nivolumab following the dose escalation part of monotherapy. In addition, Sponsor has the option to expand combination cohorts (up to 12 subjects in total per each combination cohort) at the dose previously established to be safe in order to obtain additional data or to investigate alternative dose levels to those defined in the protocol.

6 STUDY PERIODS, TREATMENT REGIMENS AND POPULATIONS FOR ANALYSES

6.1 Study Periods

- Baseline period:
 - Baseline evaluations or events will be defined as evaluations or events that occur before the date and time of the first dose of study treatment. Evaluations (laboratory tests, pulse oximetry and vital signs) on the same date and time of the first dose of study treatment will be considered as baseline evaluations. Events (AEs) on the same date and time of the first dose of study treatment will not be considered as pre-treatment events.
 - In cases where the time (onset time of event or evaluation time and dosing time) is missing or not collected, the following definitions will apply:
 - ◆ Pre-treatment AEs will be defined as AEs with an onset date prior to but not including the day of the first dose of study treatment;
 - ◆ Baseline evaluations (laboratory tests, pulse oximetry and vital signs) will be defined as evaluations with a date on or prior to the day of first dose of study treatment.
 - If there are multiple valid assessments on or prior to the first dose of study treatment:
 - ◆ For laboratory tests, the latest non missing labs value on or before first dose date (and time if collected) will be used as the baseline in the analyses. For 'LIPASE' and 'GLUCOSE', for treated subjects only, the last predose assessment with non-missing toxicity grade will be considered as baseline. If multiple assessments exist with the same collection date (and time if collected) and entry date and time, then the first observation is used as baseline.
 - ◆ For Eastern Cooperative Oncology Group (ECOG) performance status (PS), the latest ECOG PS value prior to or on the first dose date (and time if collected) will be used as the baseline in the analyses. If multiple records fall on the last date then the record with the highest value of ECOG PS will be considered as baseline.
 - ◆ For Anti-Drug Antibody (ADA), the record related to the most recent assessment among those records where date (and time if collected) of Cabiralizumab or Nivolumab immunoglobulin (IMG) assessment is less than or equal to the date (and time if collected) of the first Cabiralizumab or Nivolumab dose date.

- Post baseline period:
 - On-treatment AEs will be defined as AEs with an onset date and time on or after the date and time of the first dose of study treatment (or with an onset date on or after the day of first dose of study treatment if time is not collected or is missing). For subjects who are off study treatment, AEs will be included if event occurred within a safety window of 30 days (or 100 days depending on the analysis) after the last dose of study treatment. No “subtracting rule” will be applied when an AE occurs both pre-treatment and post-treatment with the same preferred term and grade.
 - On-treatment evaluations (laboratory tests, pulse oximetry and vital signs) will be defined as evaluations taken after the day (and time, if collected and not missing) of first dose of study treatment. For subjects who are off study treatment, evaluations should be within a safety window of 30 days (or 100 days depending on the analysis) after the last dose of study treatment.

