	D 1	D 2	D 4	D 8								
Myeloma Urine and Serum Lab tests (SPEP/UPEP/sFLC)	X				X ^f		Day 1 on every 2 cycles starting from C3D1					
Bone Marrow Aspiration/Biopsy	For confirmation of CR/sCR if applicable or, if clinically indicated at time of suspected disease progression											
Skeletal survey	If clinically indicated											
Documentation of extramedullary soft tissue plasmacytomas, if clinically indicated	As clinically indicated and at the time of CR/sCR assessments											
Flow Cytometry	For confirmation of CR/sCR if applicable or, if clinically indicated at time of suspected disease progression											
Subsequent Treatment (Anti-cancer)					X							
Survival Status					X							
Clinical Drug Supplies												
Study Drug Administration ^g	X				X		Those supplied by BMS					

^a Each cycle is 14-days.

^b End of treatment (EOT) is defined as the visit where the decision is made to discontinue the participant from treatment.

^c Physical measurements and laboratory tests do not need to be repeated if completed within the last 72 hours

^d Cycles 2-9, 13, 21

^e Cycles 2, 3, 5, 9, 13, 21

^f Only participants who have not discontinued study treatment for progressive disease.

^g Every 14 days (2days), subjects may be dosed no less than 12 days from the previous dose.

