AST or ALT >12 to $\leq 20 \times \text{ULN}$ and Total bilirubin $\leq 2 \times \text{ULN}$ or Isolated total bilirubin > 2 to $\leq 3 \times \text{ULN}$	
 – Delay cabiralizumab therapy per protocol – Increase frequency of monitoring (including but not limited to) of AST, ALT, bilirubin, alkaline phosphatase and INR (every 48-72 hours or more frequently, as clinically indicated) – Monitor for other clinical symptoms (fatigue, nausea, vomiting, abdominal pain, fever, rash, and/or eosinophilia) – Consider imaging to rule out obstruction 	
If AST and ALT $\leq 12 \times \text{ULN}$ for ≤ 28 days:
 
 – Resume routine monitoring – Resume cabiralizumab therapy at same dose level per protocol 
If elevations persist at same level for > 28 days or worsen:
 
 – Discontinue cabiralizumab therapy per protocol – Discuss with Medical Monitor
AST or ALT $> 20 \times \text{ULN}$ or Total bilirubin $>3 \times \text{ULN}$	
 – Discontinue cabiralizumab therapy 	
 – Continue LFT monitoring per protocol until resolution – Continue monitoring for and other associated clinical signs or symptoms

Hepatic Adverse Event Management with Liver Metastasis		
Grade of Liver Test Elevation	Management	Follow-Up
AST or ALT $>3.0 \times \text{ULN}$ and Total bilirubin $>2 \times \text{ULN}$ or INR > 1.5	
 – Discontinue cabiralizumab therapy per protocol 	
 – Continue LFT monitoring per protocol until resolution. – Continue monitoring for and other associated clinical signs or symptoms – Contact the Medical Monitor – Evaluate for non drug related causes of the laboratory abnormalities (e.g. obstruction, viral infection, Gilbert's disease, etc) – Under selected circumstances (e.g alternative etiology is identified), patient may receive additional therapy only after consultation and agreement between the Sponsor/MM and the investigator if receiving additional treatment with cabiralizumab is in the best interest of the patient (e.g if the subject has demonstrated a response to therapy)

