APPENDIX 8 LABORATORY ABNORMALITIES MANAGEMENT TABLE

Laboratory Abnormalities Management (CK and LDH)		
Grade of Liver Test Elevation	Management	Follow-Up
CK > 10 xULN	
 – Consider measuring CK isoenzymes as clinically indicated 	
If CK isoenzymes are abnormal
 
 – Consider checking troponin levels – Consider other assessments (including uromyoglobin) as clinically indicated 
If CK isoenzymes are normal
 
 – Continue dosing, per protocol – Monitor CK level as clinically indicated
CK or LDH > 15 to \leq 20 xULN	
 – Delay cabiralizumab and nivolumab therapy per protocol^a – Measure CK isoenzyme panel to identify source of elevation – Increase frequency of monitoring (every 48-72 hours, or more, as clinically indicated) – Notify the Medical Monitor 	
If returns to \leq 15 xULN within \leq 28 days:
 
 – Resume routine monitoring, resume cabiralizumab and nivolumab therapy at same dose level per protocol – If CK isoenzyme panel is normal continue monitoring the subject. – If CK isoenzyme panel is abnormal then consider measuring troponins. – If troponins are abnormal, contact Medical Monitor to determine if the subject can be retreated. 
If elevations persist at the same level > 28 days or worsen:
 
 – Discontinue further dosing – Discuss with Medical Monitor
CK or LDH > 20 xULN	
 – Discontinue cabiralizumab and nivolumab therapy 	
 – Follow up until resolution

a. If the AE requiring dose delay was due to one of the study drugs, the non-offending drug may be continued, taking into account the safety and clinical benefit to the patient.

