7.1.2 Laboratory Tests

Clinical laboratory parameters (hematology, serum chemistry and electrolytes) will be evaluated.

Laboratory tests will be graded using the NCI Common Terminology Criteria, and the most recent version of the criteria at the time of the database lock will be used.

Clinical laboratory data will be analyzed using International System of Units (SI).

In the laboratory summary tables, unless otherwise specified, subjects will be counted only once for each lab parameter according to their worst on treatment CTC grade (worst being the highest CTC grade). The laboratory tables and listings will be sorted by laboratory category, laboratory subcategory and laboratory test code sequence number.

7.1.3 *Immunogenicity Data*

Blood samples for immunogenicity analysis will be collected from subjects according to the protocol schedule. Samples will be evaluated for development of Anti-Drug Antibody (ADA).

7.2 *Study Conduct*

Enrollment by country and site will be summarized and listed for all enrolled subjects.

A by-subject listing of batch numbers for all treated subjects will be provided.

7.3 *Study Population*

Analyses in this section will be tabulated for all enrolled subjects by cohort, unless otherwise specified.

7.3.1 *Subject Disposition*

The total number of subjects enrolled (treated or not treated) will be presented along with the reason for not being treated. This analysis will be performed on the all enrolled subjects population only.

Number of subjects who discontinued study treatment along with corresponding reason will be tabulated by cohort. Reason for discontinuation will be derived from subject status CRF page. This analysis will be performed only on the all treated subjects population.

A by-subject listing for all treated subjects will be provided showing the subject's off treatment date and whether the subject continue in the treatment period/study along with the reason for going off treatment period/study. A by-subject listing for all enrolled subjects will also be provided, showing whether the subject was treated along with the reason for not being treated.

7.3.2 *Demographics and Other Baseline Disease Characteristics*

The following demographic and baseline characteristics will be summarized and/or listed by cohort:

Solid Tumor (Cohort M1, M2, and C1)

Summary:

The following subject demographics and baseline characteristics will be summarized for all treated subjects by cohort.

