The analysis population for each laboratory test is restricted to treated subjects who underwent that laboratory test. Laboratory tests (in addition to the tests specified below) with CTC criteria collected in the specific studies may also be included in the summaries.

7.6.6.1 *Hematology*

The following will be summarized by cohort as worst CTC grade on-treatment per subject and as shift table of worst on-treatment CTC grade compared to baseline CTC grade per subject: hemoglobin (HB), platelets, white blood counts (WBC), absolute neutrophils count (ANC) and lymphocyte count (LYMPH).

The analyses will be conducted using the 30-day safety window.

A by-subject listing of these laboratory parameters will be provided.

7.6.6.2 *Serum Chemistry*

The following will be summarized by cohort as worst CTC grade on-treatment per subject and as shift table of worst on-treatment CTC grade compared to baseline CTC grade per subject: ALT, AST, alkaline phosphatase (ALP), total bilirubin and creatinine.

The analyses will be conducted using the 30-day safety window.

A by-subject listing of these laboratory parameters will be provided.

7.6.6.3 *Electrolytes*

The following will be summarized by cohort as worst CTC grade on-treatment per subject and as shift table of worst on-treatment CTC grade compared to baseline CTC grade per subject: sodium (high and low), potassium (high and low), calcium (high and low), magnesium (high and low), and Glucose Serum (fasting hyperglycemia and hypoglycemia regardless of fasting status)

The analyses will be conducted using the 30-day safety window.

A by-subject listing of these laboratory parameters will be provided.

7.6.6.4 *Abnormal Hepatic Test*

Summary:

The number (%) of subjects with the following laboratory abnormalities from on-treatment evaluations will be summarized by treatment group, provided at least 5 subjects with an abnormality within at least one treatment group. Otherwise, only listing and plot will be provided:

- ALT or AST > 3 x ULN, > 5 x ULN, > 10 x ULN, > 12 x ULN and > 20 x ULN
- Isolated Total bilirubin > 2 to \leq 3 x ULN
- ALT or AST > 20 x ULN or Total bilirubin > 3 x ULN
- Concurrent (within 3 days) ALT or AST > 3 x ULN and Total bilirubin > 2 x ULN
- Concurrent (within 3 days) ALT or AST > 5 to \leq 12 x ULN and Total bilirubin \leq 2 x ULN
- Concurrent (within 3 days) ALT or AST > 12 to \leq 20 x ULN and Total bilirubin \leq 2 x ULN

Figure:

- Scatter plot of Total bilirubin peak vs AST peak

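### The 30-day laboratory window can drop a new worst value reached late in a dosing hold if the subject is then discontinued, although the same value counts if dosing resumes

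*SAP*

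**What the plan says.** SAP 6.1 defines on-treatment laboratory values as "evaluations taken after the day (and time, if collected and not missing) of first dose of study treatment". It then adds a limit: "For subjects who are off study treatment, evaluations should be within a safety window of 30 days (or 100 days depending on the analysis"), counted from the last dose. No upper limit is set for anyone else. SAP 7.1.2 counts each subject once per parameter, "according to their worst on treatment CTC grade (worst being the highest CTC grade").

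For hematology, serum chemistry and electrolytes, SAP 7.6.6.1 to 7.6.6.3 each choose the shorter window: "The analyses will be conducted using the 30-day safety window". None of these tables is repeated at 100 days. SAP 7.6.6.4, on abnormal hepatic tests, refers to on-treatment evaluations without naming a window.

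The protocol allows holds that outlast 30 days. In the Appendix 6 hepatic hold rows (monotherapy), treatment is stopped "If elevations persist at same level for > 28 days or worsen". Appendix 8 has the matching condition for CK and LDH: "If elevations persist at the same level > 28 days or worsen". Protocol 8.1.1 sets a general limit of 6 weeks from the previous dose, and longer delays are possible for drug-related events. Footnote b of Table 2-2 states: "End of treatment (EOT) is defined as the visit where the decision is made to discontinue the participant from treatment". Laboratory tests are scheduled at that visit.

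**The concern.** The cut-off runs from the last dose, but the decision to discontinue can come well after it. For a subject who resumes, the last dose falls after the hold, so every hold value is inside the on-treatment period. For a subject who never resumes, the last dose is the one before the hold, and values beyond day 30 drop out. Whether a given value is included depends on what happens after it was measured.

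Laboratory abnormalities in the monotherapy cohorts are a component of the primary endpoint (Protocol Table 4-1). Leaving values out can only lower a subject's worst grade or leave it unchanged. Any loss falls on subjects who stopped treatment after a hold. The cohorts are small, so one subject is 1/6 = 16.7 percentage points of a cohort of 6 and 1/3 = 33.3 points of a cohort of 3.

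**Working it through.** The plan gives no figure to reproduce here. The check is date arithmetic on its own rules.

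**Inputs**
- Cut-off for discontinued subjects: day 30 after the last dose (SAP 6.1, 7.6.6.1 to 7.6.6.3).
- Hold limit: 28 days at the same level, or worsening (Protocol Appendix 6).
- Day the hold starts, *s*, counted from the last dose. The Cycle 1 Day 8 draw gives *s* = 7. The pre-dose draw of the next cycle may be taken up to 72 hours before a dose given at 14 ± 2 days. That gives *s* from 14 − 2 − 3 = 9 to 14 + 2 = 16, nominally 14 (Table 2-2).
- Monitoring during a hepatic hold: every 48 to 72 hours or more often (Appendix 6).

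**Hold days outside the window**

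The 28-day limit falls on day *s* + 28, so days outside = *s* + 28 − 30.

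| Hold starts (day) | 28-day limit (day) | Days inside | Days outside | Share of 28 |
|---|---|---|---|---|
| 7 | 35 | 23 | 5 | 18% |
| 9 | 37 | 21 | 7 | 25% |
| 12 | 40 | 18 | 10 | 36% |
| 14 | 42 | 16 | 12 | 43% |
| 16 | 44 | 14 | 14 | 50% |

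If the subject resumes, 0 days are lost in every row. A delay of 6 weeks (42 days) puts 42 − 30 = 12 days outside. At one draw every 2 to 3 days, those 12 days hold about 12/3 = 4 to 12/2 = 6 hepatic draws, so the excluded values do exist.

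**When a peak is lost**

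I applied the SAP rule to four assumed transaminase courses, with draws every 3 days from day 14. The table gives the worst value counted, in multiples of ULN.

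| Course (assumed) | Discontinued, 30-day window | Resumed | 100-day window |
|---|---|---|---|
| 13, rising to 22 from day 35 | 13 | 22 | 22 |
| 13, rising to 22 from day 20 | 22 | 22 | 22 |
| 15 throughout | 15 | 15 | 15 |
| 22 on day 14, then 18 | 22 | 22 | 22 |

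Only the first course loses its peak. The resumed column shows how the SAP rule would treat the same values. Under Appendix 6 a subject who worsened in this way would ordinarily be discontinued, so the first column is the one to expect in practice. Whether the move from 13 to 22 changes the worst-grade table depends on CTC grade limits for ALT and AST, which the documents do not reproduce. It does cross the 20 × ULN cut-point that SAP 7.6.6.4 tabulates.

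**The case against.** A reader might infer that the tables generally lose the values that ended treatment. The documents do not support that.

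- Some values stop treatment at once, such as AST or ALT above 20 × ULN (Protocol 8.1.1, Appendix 6). Found at a scheduled draw 7 to 16 days after the last dose, they are inside the window.
- Persistence at the same level loses duration but not the peak, which was recorded when the hold began.
- Worsening before day 31 is counted.

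Nor does the 28-day scenario reach every parameter.

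- **Creatinine:** the renal rows in Appendix 7 move to discontinuation after 14 days or on worsening. That is 14 + 14 = day 28 from the nominal draw, and day 30 from the latest (day 16).
- **Blood counts:** Appendices 6 to 8 have no 28-day row. The 7-day limits in 8.1.1 give 14 + 7 = day 21.
- **Combination hepatic holds:** Appendix 7 already stops further dosing after 7 days, again about day 21, although nivolumab may be considered.
- **CK and LDH:** they are not among the parameters named in SAP 7.6.6.2 and enter only if added as further tests.
- **SAP 7.6.6.4:** with no window named, an effect there cannot be determined.

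Other outputs also carry some of the information. Abnormalities that interrupt or stop treatment must be recorded as adverse events (Protocol 9.2.6). Drug-related events are repeated at 100 days (SAP 7.6.4). AST, ALT and CK abnormalities are events of interest summarised at 100 days (SAP 7.1.1.1, 7.6.5). By-subject laboratory listings are planned.

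All of this stands and narrows the point. It does not repair the laboratory tables. The event tables depend on investigator reporting and, for the repeated 100-day table, on causality. Bilirubin is not among the event-of-interest categories named, and a listing is not a summary.

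**Conclusion.** The asymmetry follows from the stated rule, and nothing elsewhere in the SAP removes it. A peak is lost only under three conditions together: a new maximum is first reached more than 30 days after the last dose, the subject is then discontinued, and the value crosses a CTC grade boundary. The main setting is a monotherapy ALT, AST or bilirubin hold under Appendix 6, or a delay running to or past 6 weeks under 8.1.1.

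The range of 5 to 14 hold days (18% to 50% of 28) assumes that the hold starts at a scheduled draw and runs its full 28 days. It is tempting to read 43% as a share of peaks or subjects, but it counts days at the nominal draw. The documents give no frequency for the qualifying sequence, so the number of subjects affected cannot be computed. The direction is certain: a reported worst grade can only be too low. This is a modest defect, worth correcting because the correction is cheap.

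**What to change.** Either of two changes to the SAP would do.

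1. In 6.1, end the on-treatment period for laboratory evaluations at the later of last dose plus 30 days and the end-of-treatment visit. Hold values up to the decision then count whether or not dosing resumes. In the first course above, an end-of-treatment visit on or after day 35 brings the 22 × ULN value into the table. The window then varies by subject, and it also lengthens when the decision is late for reasons other than toxicity.
2. Keep 6.1 and repeat the 7.6.6.1 to 7.6.6.3 worst-grade and shift tables with the 100-day window it already defines. This covers a 28-day hold (ending by day 44) and a 6-week delay. A delay beyond 100 days would still be cut.

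In either case, state the same window explicitly for 7.6.6.4.

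The cost is a derivation change and a little extra programming on data already collected. No clinical rule changes. Some later values not caused by the drug may be included, and reported worst grades may be slightly less favourable.
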